### Study Period 1: Randomized controlled trial:

- 8 subjects randomized to PRP
- 5 subjects randomized to control.
- 

Patients will be randomized to standard treatment procedures versus standard treatment plus intrauterine infusion of platelet rich plasma (PRP). Both groups of patients will receive the same initial workup, consultation and evaluation, treatment, surgical interventions or cycle monitoring, ultrasounds and embryo transfer. The only difference between the two groups will be the intrauterine infusion of PRP based on randomization and that the experimental group will have an extra blood draw for PRP preparation.

The only difference in clinical practice that the experimental group in this randomized controlled trial would have that differed from the "control" population, would be the 1-2 intrauterine infusion of PRP based on randomization and that the experimental group will have an extra blood draw for PRP preparation. The standard of care procedures for patients with Asherman's Syndrome is as following.

All patients will undergo the hysteroscopic procedure in the operating room under general anesthesia for resection of intrauterine adhesions. The degree of the adhesions will be rated by the physician performing the surgery using ASRM classification guidelines. The scar and adhesions will be resected with hysteroscopic scissors and grasper, until the endometrium appears to be reached with visualization of vascularity. Thereafter, a pediatric 8-10-gauge Foley catheter will be placed into the uterine cavity, and the balloon will be inflated with 3 ml of normal saline. The catheter extending out of the uterus will be tied off with 2 ties of 2'0' silk and then the catheter will be cut distally to the knots, with no parts extending outside of the vagina. Patients will be discharged home the same day and instructed to start on 30 days of 2 mg estradiol twice daily per usual protocol, with 10 days of medroxyprogesterone acetate 10mg daily for the last 10 days of estradiol. All patients will receive doxycycline antibiotic 100mg twice a day for the duration of the intrauterine Foley catheter placement (5-7 days). They will have endometrial lining assessment with transvaginal ultrasound 2 and 4 weeks during the first month post-procedure. Second look hysteroscopy will be performed after 1 month to assess the uterine cavity. Patients will be asked to record the menstrual flow diary before treatment and for the next 1-3 months (Menstrual Assessment Chart, from Higham et al, BJOG 1990). Future fertility treatment will be planned on individual bases per patients' preferences. For the patients with thin endometrial lining, the standard of care guidelines for hormone replacement in the setting of frozen IVF cycles will be used as a reference (not a part of experimental protocol) chosen by the primary physician. The primary doctor will manage the entire hormone replacement based on the clinical knowledge, expertise and standard of care practices. Endometrial lining measured by ultrasound is recorded at every visit. Patients will be undergoing standard controlled frozen embryo transfer (FET) cycle and will be started on oral contraceptive pills (OCP, Desogen) to block the endogenous hormone production for 14-28 days, per usual protocol. GnRH agonist (Leuprolide acetate, Lupron) will be started for pituitary suppression 6-7 days before the last OCP dose, subcutaneously at a dose of 10 units (0.5mg) daily, which will continue until start of progesterone. Patients will present for baseline ultrasound per standard

practice on second day of menses after OCP withdrawal. If baseline ultrasound normal, patients will start Vivelle estradiol patch 0.1mg every 36 hours with increasing dose, again per standard protocol. Surveillance ultrasound lining check will be scheduled on cycle day 12. Per our standard protocol, minimal endometrial strip thickness of 7mm is required before initiation of progesterone. If patients meet the criteria for embryo transfer, it will be performed according to the standard of care. If the lining is thin, patient will be randomized to control or study group.

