7.11 INSTRUMENTS: List all questionn

Study period 2 (10/2/2018):

Prospective recruitment of patients opting for PRP (no randomization; all received intervention.).

- 14 Subjects received PRP using the above protocol

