Platelet-rich Plasma (PRP) for Endometrial Regeneration and Repair NCT02825849

Document Date: Nov 15, 2020

Summary of PRP Study Protocol

Statistical Analysis Plan:

This study was a small, first-in-human pilot study of the use of Platelet Rich Plasma in women with either Asherman's syndrome or think uterine lining. Our over-arching goal was to establish the feasibility of administering and study the impact of PRP in a fertility clinic setting. The primary outcome of this study was improvements in uterine lining. Our secondary outcome was pregnancy rate. We ultimately enrolled 17 subjects into the intervention arm and 5 subjects into the control arm. This study was not powered to detect statistically significant differences. Accordingly, we have calculated and presented descriptive statistics of our baseline characteristics and study outomes. In particular, we have calculated means and standard deviation for continuous outcomes and percentages for dichotomous outcomes.

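### Some average rise in lining is expected without PRP, so the uncontrolled Period 2 women cannot inform PRP's impact and should not be pooled against the five randomized controls

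*Protocol*

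**What the plan says.** **Entry, thin-lining route** (Protocol, Study Period 1). After the baseline scan, "patients will start Vivelle estradiol patch 0.1mg every 36 hours with increasing dose, again per standard protocol". Then "Surveillance ultrasound lining check will be scheduled on cycle day 12". The rule for going on is that a "minimal endometrial strip thickness of 7mm is required before initiation of progesterone". For the rest, "If the lining is thin, patient will be randomized to control or study group". This is the only randomization trigger in the text shown. The primary doctor manages hormone replacement.

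**Asherman's route** (same section). Adhesions are resected by hysteroscopy, followed by 30 days of estradiol, lining scans at 2 and 4 weeks, and a second-look hysteroscopy after 1 month.

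**Period 1** randomized 8 women to PRP and 5 to control.

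**Period 2** (Protocol, Study period 2) is described as "Prospective recruitment of patients opting for PRP (no randomization; all received intervention". Fourteen women received PRP under the protocol already described.

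**SAP.** "The primary outcome of this study was improvements in uterine lining". No reference scan, time point or definition of improvement is given. The goal covers both feasibility and PRP's impact. Enrolment is given as 17 intervention and 5 control, without separating the periods. The study is called an unpowered pilot, and the analysis is descriptive: means, standard deviations and percentages.

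**The concern.** The primary outcome is a change, and other things besides PRP can move it in the same direction. A woman who enters on a low reading tends, on average, to read higher next time. Progesterone waits for 7 mm, so a thin lining also means a longer estrogen phase. After adhesion surgery, the resection and a month of estradiol may themselves improve the lining. In Period 1 the controls share all of this. In Period 2 nobody does.

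If the 17 are summarised as one arm, the mean improvement contains an unknown amount of non-PRP change. A comparison with the 5 controls would also set mostly self-selected, later recruits beside randomized ones. Describing the result without a test does not help: lack of power is random error, and this is bias. A reader would take the mean improvement as the pilot's evidence of impact, and it could well be positive if PRP did nothing.

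**Working it through.** **1. The SAP's own figure.** PRP recipients by the protocol's counts: 8 + 14 = 22, against 17 in the SAP. All women: 8 + 5 + 14 = 27, against 22. Neither reproduces. Both gaps are 5 and would close if five Period 2 women had already been counted in Period 1, but the documents do not say so.

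**2. How much of the intervention arm is uncontrolled.** Period 1 can supply at most 8 of the 17, so at least 17 - 8 = 9 (9/17 = 53%) come from outside the randomized PRP arm. Period 2 is the only other source described. On the protocol's counts the share is 14/22 = 64%.

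**3. Non-PRP change on each route.** For thin lining, baseline is "practice on second day of menses after OCP withdrawal", so the day-12 scan falls about 10 days into escalating estradiol, and a woman below 7 mm stays in the estrogen phase. For Asherman's syndrome, resection and 30 days of estradiol are standard care. Neither route needs an assumed number to show that lining may change without PRP.

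**4. Possible size of regression to the mean (assumed inputs, none in the documents).** Take two scans as bivariate normal with common mean m, SD s = 2 mm and correlation r. Select women with the first scan below 7 mm, and assume no PRP effect and no further estrogen effect.

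- a = (7 - m)/s
- mean of the selected first scan = m - s × φ(a)/Φ(a)
- expected rise = (1 - r) × s × φ(a)/Φ(a)
- share at or above 7 mm on the second scan = 1 - Φ₂(a, a; r)/Φ(a)

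Example, m = 7, r = 0.5: a = 0, φ/Φ = 0.3989/0.5 = 0.798, rise = 0.5 × 2 × 0.798 = 0.80 mm, share = 33%.

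| Assumed mean | Rise, r = 0.5 | Rise, r = 0.8 | Rise, r = 0.9 | Share ≥ 7 mm, r = 0.5 | r = 0.8 | r = 0.9 |
|---|---|---|---|---|---|---|
| 5 mm | 0.29 | 0.12 | 0.06 | 11% | 7% | 5% |
| 6 mm | 0.51 | 0.20 | 0.10 | 21% | 13% | 9% |
| 7 mm | 0.80 | 0.32 | 0.16 | 33% | 20% | 14% |
| 8 mm | 1.14 | 0.46 | 0.23 | 47% | 29% | 20% |
| 9 mm | 1.53 | 0.61 | 0.31 | 61% | 38% | 27% |

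The rise is positive throughout, from 0.06 to 1.53 mm. Any effect of continuing estradiol comes on top.

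**5. What the randomized comparison can offer.** The 95% interval for a difference in mean change, 8 v 5, has half-width t(0.975; 11) × √(1/8 + 1/5) = 2.201 × 0.570 = 1.25 SD of change. With an assumed mean of 7 mm, SD 2 mm and r = 0.7, the SD of change is about 1.47 mm, so the half-width is about 1.25 × 1.47 = 1.8 mm. It is free of the shared drift, but imprecise.

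**The case against.** The strongest reply is that the SAP already limits itself: a first-in-human pilot, unpowered, descriptive, with feasibility in its goal and no test or efficacy claim for Period 2. That stands for the feasibility aim. It does not cover the impact aim, which carries no caveat about drift and is reported on an arm that is mostly uncontrolled.

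Several stronger readings are tempting, and the documents do not support them.

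- *Women enter on one unconfirmed scan.* No repeat scan or failed earlier cycle is required in the text shown, but no eligibility section is visible, linings are recorded at every visit, and thin-lining patients are mentioned before the cycle is described. A known history would make regression smaller.
- *Period 2 used the same entry rule, and day 12 is the baseline.* The reference to the protocol above may describe only the treatment, and the SAP names no reference scan. The regression figures apply only if both inferences hold.
- *Estradiol is still rising after entry.* The schedule beyond day 12 is not given. Continued exposure is the most that can be said.
- *Every woman improves, or most reach 7 mm, without PRP.* Regression to the mean is an average effect. In the table only one of the 15 shares exceeds 50%.
- *The day-12 mechanism covers all women.* Women with Asherman's syndrome may have entered at surgery, and the split by condition is not given.

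A woman's peak lining in an earlier cycle is not a safe substitute for a control. Such scans may not exist, a peak set against a later single scan brings its own bias, and surgery may lie in between.

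**Conclusion.** The point holds in a limited form. Some average rise in lining is expected without PRP, and Period 2 has nothing to separate PRP from it. At least 9 of the 17 intervention women therefore cannot inform impact, and pooling them against the 5 controls gives up the protection of randomization. This conclusion rests on the documents' design and counts, not on assumed figures.

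The size of the drift is not known. Regression to the mean alone could be about 0.1 to 1.5 mm, with about 5% to 61% of women reaching 7 mm, if the assumed distribution and the day-12 baseline apply. The low end corresponds to women whose linings are habitually thin.

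None of this shows that PRP is without effect, and it does not undermine the feasibility aim. The drift does not bias the randomized 8 v 5 comparison in expectation; the limit there is precision.

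**What to change.** In the SAP:

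1. Base any statement about PRP's impact only on the Period 1 randomized comparison (8 v 5). Show the change in each arm over the same stated interval, and the between-arm difference with a 95% confidence interval.
2. Report Period 2 separately, as feasibility and as combined change on standard care plus PRP, with no impact claim.
3. Do not pool Period 2 with the Period 1 PRP arm against the 5 controls. State how many of the 17 belong to each period, which also requires reconciling 17 with 8 + 14.

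This needs no new patients, scans or change in care: it is SAP wording and a re-tabulation of recorded data, and it can be done although enrolment has ended. The price is an interval about ±1.25 SD of change wide and a more cautious conclusion. That is a fair account of what 13 randomized women can show.

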7.11 INSTRUMENTS: List all questionn

Study period 2 (10/2/2018):

Prospective recruitment of patients opting for PRP (no randomization; all received intervention.).

- 14 Subjects received PRP using the above protocol

Platelet-rich Plasma (PRP) for Endometrial Regeneration and Repair NCT02825849

Document Date: Nov 15, 2020

Summary of PRP Study Protocol

Statistical Analysis Plan:

This study was a small, first-in-human pilot study of the use of Platelet Rich Plasma in women with either Asherman's syndrome or think uterine lining. Our over-arching goal was to establish the feasibility of administering and study the impact of PRP in a fertility clinic setting. The primary outcome of this study was improvements in uterine lining. Our secondary outcome was pregnancy rate. We ultimately enrolled 17 subjects into the intervention arm and 5 subjects into the control arm. This study was not powered to detect statistically significant differences. Accordingly, we have calculated and presented descriptive statistics of our baseline characteristics and study outomes. In particular, we have calculated means and standard deviation for continuous outcomes and percentages for dichotomous outcomes.

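### The primary lining outcome names no scan or baseline and counts women by arm only, so a 17 v 5 summary can mix two indications, different hormonal settings and two study periods

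*SAP*

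**What the plan says.** **SAP.** The primary outcome is given as "The primary outcome of this study was improvements in uterine lining". The population has either Asherman's "syndrome or think uterine lining" (evidently thin lining). Numbers are given by arm only: "We ultimately enrolled 17 subjects into the intervention arm and 5 subjects into the control arm". The analysis is one general rule: "we have calculated means and standard deviation for continuous outcomes and percentages for dichotomous outcomes". The SAP names no scan, no baseline and no presentation by indication or study period.

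**Protocol, Study Period 1, care after adhesion resection.** Oral estradiol runs for 30 days, "with 10 days of medroxyprogesterone acetate 10mg daily for the last 10 days of estradiol". On scans: "They will have endometrial lining assessment with transvaginal ultrasound 2 and 4 weeks during the first month post-procedure".

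**Protocol, Study Period 1, thin lining.** "Endometrial lining measured by ultrasound is recorded at every visit". In the frozen-transfer cycle there is an ultrasound labelled baseline on day 2 of menses, before the estradiol patch starts, and a lining check on cycle day 12 while on the patch. A woman whose lining is thin is then randomised. The 7 mm threshold is a condition for starting progesterone and is not tied to the outcome.

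**Protocol, numbers.** Period 1 has "8 subjects randomized to PRP" and 5 to control. Period 2 adds 14 women who chose PRP, without randomisation.

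**The concern.** Lining thickness depends on the hormones a woman is taking when she is scanned. The protocol yields several candidate scans per woman in different settings, and the SAP does not say which one carries the primary result or what it is compared with. If results are tabulated by arm alone, the PRP and control figures may be averages over different blends of indication, hormonal phase and study period.

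Within an indication, both randomised arms receive the same background care, so the distortion comes from a difference in blend between arms. With 5 controls, a difference in blend can easily be large. The Period 2 women have no concurrent control, and their indication mix was not set by randomisation. At stake is whether a reader can tell what the primary result measures, and whether a difference between arms could be anything other than case mix.

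**Working it through.** **1. The SAP's count.** Protocol PRP women: 8 (Period 1) + 14 (Period 2) = 22. The SAP gives 17, so it is not reproduced; the gap is 22 − 17 = 5. Controls agree at 5. Totals are 22 + 5 = 27 in the protocol and 17 + 5 = 22 in the SAP. If the 17 are drawn from the protocol's 22, at most 8 were randomised to PRP, so at least 17 − 8 = 9 were not.

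**2. Hormonal phase after resection.** With 30 days of estradiol and progestin in the last 10, the progestin days are 21 to 30. Assume estradiol starts about the day of surgery. The 2-week scan is then near day 14, on estradiol only, and the 4-week scan is near day 28, within the progestin days. If estradiol started k days later, the 4-week scan would fall near day 28 − k, which stays at 21 or above for a delay of up to about 7 days.

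**3. The settings side by side.**

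| Scan | Setting | Role in the primary outcome |
|---|---|---|
| 2 weeks after resection | oral estradiol only | not stated |
| 4 weeks after resection | estradiol plus progestin (step 2) | not stated |
| Day 2 of transfer cycle | before the estradiol patch | called baseline, but not for the outcome |
| Day 12 of transfer cycle | on the patch, before progesterone | precedes randomisation if lining is thin |

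Change from day 2 includes growth on estradiol that would occur without PRP. Change from day 12 starts from a value selected for being thin, so it is open to regression to the mean. A randomised comparison using the same scans in both arms shares that effect. Period 2 has no concurrent control to share it.

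**4. Difference between arms with no PRP effect.** Let y of the 17 PRP women and x of the 5 controls have Asherman's syndrome, and let D be the mean lining result in Asherman's women minus that in thin-lining women. The by-arm difference is then

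(y/17 − x/5) × D.

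Moving one control between indications changes this by 1/5 = 0.20 D; moving one PRP woman changes it by 1/17 = 0.06 D. The documents give none of x, y or D. For assumed values of y, over all possible x:

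| Assumed y | x = 0 | x = 5 |
|---|---|---|
| 6 | +0.35 D | −0.65 D |
| 8 | +0.47 D | −0.53 D |
| 11 | +0.65 D | −0.35 D |

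These rows show how the artefact scales and are not estimates. Between the extremes it can be near zero: with y = 8 and x = 2 it is 8/17 − 2/5 = +0.07 D.

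**5. Cell size.** If both indications are among the 5 controls, the smaller cell holds 1 or 2 women.

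**The case against.** Several points on the other side are fair.

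- **Outcome type.** The SAP has two outcomes and two summary rules. Lining is measured in mm and pregnancy is a rate, so mean and SD for lining is the natural reading. A reader might infer that the outcome type is wholly undefined; that goes too far. What remains open is whether the mean is of change or of follow-up thickness, and from which scan.
- **Pooling.** A reader might infer that the SAP pools the indications. It does not say so; its wording only permits it.
- **Separate settings.** The split is partly inferred. The protocol leaves later fertility treatment to individual planning and then describes a transfer cycle, so some Asherman's women may also have day-2 and day-12 scans. This adds to the scans that need naming.
- **Period 2 baseline.** Those women had no scan at randomisation, but the protocol says the same procedures were followed, so an equivalent qualifying scan may exist.
- **Descriptive pilot.** The SAP claims no power and describes no test. This removes any argument about type I error or lost power. A descriptive mean still needs a defined variable and time point.
- **Incomplete text.** The available protocol text breaks off at its instruments section, so a definition elsewhere cannot be excluded. The point concerns the SAP, which should carry it.

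It is also tempting to attach a probability of chance imbalance in indication mix, or a bias in mm. The documents support neither: they give no indication counts and no lining results, and a chance model does not describe women who chose PRP.

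**Conclusion.** The point holds, as a reporting weakness in the primary outcome. The SAP leaves the scan and baseline unnamed and counts women by arm only. The arms can therefore combine different indications and hormonal phases, and can set non-randomised PRP women against controls who all come from randomised Period 1.

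The possible artefact is the mix difference times the difference in mean result between indications. Its size in mm cannot be derived, and it may be small if the mixes happen to agree. Placing the 4-week scan in the progestin days assumes that estradiol starts about the day of surgery. The minimum of 9 women not randomised to PRP assumes that the SAP's 17 are drawn from the protocol's 22. Since the counts do not reconcile, a reader should not treat any share of non-randomised women as established.

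**What to change.** Change analysis and reporting only; care is unaffected.

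1. Report n and lining results by arm, indication and study period. Show the randomised Period 1 comparison separately from Period 2.
2. Do not pool 4-week progestin-phase scans with scans taken on estrogen alone.
3. For each indication, state which scan is the outcome, which pre-PRP scan is the baseline, and whether the result is change in mm or follow-up thickness. Label any choice made now as post hoc. Note that change from a scan selected for being thin is open to regression to the mean, with no concurrent control in Period 2.
4. Reconcile the protocol's 22 PRP women with the SAP's 17, and show how many of the 17 come from each period.

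The cost is a few sentences in the SAP and a re-cut of existing measurements. The protocol says lining is recorded at each visit, but the documents do not confirm that every scan was obtained, so report what is available. The drawback is very small cells: the results remain descriptive, and any subject-level listing needs care over re-identification.

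### The SAP's single intervention arm of 17 combines 8 or fewer randomised PRP women with at least 9 who were not randomised to PRP, is set beside 5 randomised controls, and does not agree with the Protocol's 8 + 14 = 22

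*SAP*

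**What the plan says.** The Protocol describes two parts.

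- **Study Period 1** is a randomised trial: "8 subjects randomized to PRP" and "5 subjects randomized to control". The same section says of these groups: "The only difference between the two groups will be the intrauterine infusion of PRP based on randomization", together with the extra blood draw needed to prepare the PRP.
- **Study period 2**, dated 10/2/2018 and printed under the 7.11 Instruments heading, is described as "Prospective recruitment of patients opting for PRP (no randomization; all received intervention". Its count is "14 Subjects received PRP using the above protocol". It has no control group.

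The SAP, dated Nov 15, 2020, mentions neither period. It names improvement in uterine lining as the primary outcome and continues: "Our secondary outcome was pregnancy rate. We ultimately enrolled 17 subjects into the intervention arm and 5 subjects into the control arm". It says the study was not powered, and that the results are descriptive: means and standard deviations for continuous outcomes and "percentages for dichotomous outcomes".

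**The concern.** The SAP presents two arms as if they had been formed in the same way. The control arm was formed by randomisation in Period 1. More than half of the intervention arm consists of women who cannot have been randomised to PRP, and Period 2 women asked for it. The Protocol's assurance that the groups differ only by the infusion and blood draw applies to the randomised women and cannot be carried over to 17 v 5.

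The SAP gives studying the impact of PRP as part of its goal, so readers will set the two arms side by side even without a test. Part or all of any gap in lining or pregnancy could reflect who chose PRP, or the period in which they were treated. Separately, an arm size that does not follow from the Protocol's own counts leaves the reader unsure whose outcomes are in the summary.

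**Working it through.** **Inputs.** Protocol, Study Period 1: 8 randomised to PRP, 5 to control. Protocol, Study period 2: 14 received PRP without randomisation. SAP: 17 intervention, 5 control.

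**1. Can the SAP's 17 be reproduced?**

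| Count | Protocol | SAP | Gap |
|---|---|---|---|
| PRP | 8 + 14 = 22 | 17 | 5 |
| Control | 5 | 5 | 0 |
| All women | 8 + 5 + 14 = 27 | 17 + 5 = 22 | 5 |

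The control count agrees; the PRP count does not. Neither 8 nor 14 alone gives 17. The Protocol's 22 PRP women and the SAP's 22 women in total are different quantities that happen to coincide.

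**2. How many of the 17 were not randomised to PRP?** Taking the 17 as distinct women:

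- Minimum: all 8 randomised PRP women are included, so 17 − 8 = 9, and 9/17 = 52.9%.
- Maximum: all 14 Period 2 women are included with no overlap, so 14/17 = 82.4%, leaving 17 − 14 = 3 of the 8 randomised women.
- If the Protocol's 22 were used instead: 14/22 = 63.6%.

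The minimum of 9 holds however the gap of 5 is explained, because only 8 women were ever randomised to PRP.

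**3. What could pooling do?** The documents give no outcome data, so this part is illustrative. Suppose PRP has no effect, and that the m women not randomised to PRP differ from the randomised women by d points in pregnancy rate. The pooled contrast then shows a spurious difference of (m/17) × d.

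| Assumed d | m = 9 | m = 14 |
|---|---|---|
| 10 points | 5.3 | 8.2 |
| 20 points | 10.6 | 16.5 |
| 30 points | 15.9 | 24.7 |

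The sign follows the sign of d, which is unknown. The same weights apply to mean lining: 53% to 82% of any underlying difference between the two kinds of women passes into the pooled contrast.

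**4. What does separation cost in precision?** Exact (Clopper-Pearson) 95% intervals for assumed counts: 2/8, 3.2% to 65.1%; 4/17, 6.8% to 49.9%; 1/5, 0.5% to 71.6%.

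**The case against.** The strongest reply is that the SAP calls this a small first-in-human pilot with feasibility as part of its goal, declares it unpowered and plans no test. That stands as far as it goes: no p-value or formal effect estimate is affected, and the stakes are lower than in a confirmatory trial. But lack of power concerns chance, whereas pooling concerns bias, and leaving out a test does not make the 17 and the 5 comparable.

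A second reply also has force. With 5 controls, the 8 v 5 description is numerically no more informative than 17 v 5. The gain is that the comparison means what its label says.

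Four stronger readings are tempting and are not supported:

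- *That the SAP reports a pregnancy percentage for 17 v 5.* It gives enrolment counts and, separately, says percentages were calculated. It states no pregnancy denominator and no between-arm contrast. Pooling is the plain reading, not a stated fact.
- *That the gap of 5 arose because the 5 controls later took PRP.* The arithmetic would fit (8 + 9 = 17), but nothing in the text says any control received PRP.
- *That pooling favours PRP.* The direction cannot be determined.
- *That no explanation of the counts exists.* Part of the Protocol is not in the text available for review and the 7.11 heading is cut off, so one may exist elsewhere.

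**Conclusion.** The point holds as a reporting fault that should be corrected. At least 9 of the 17 (53%), and at most 14 (82%), were not allocated to PRP by randomisation, while all 5 controls were. A 17 v 5 summary of either lining or pregnancy would therefore be confounded by self-selection and study period. The PRP counts of 22 and 17 disagree by 5, and the available text does not explain why.

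The head counts assume that the 17 are distinct women and that the Protocol's counts of 8, 5 and 14 are right. That the outcomes are actually pooled is inferred from the SAP naming two arms and making no separation by period. The size of any distortion is unknown; the figures for it above depend wholly on assumed differences.

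**What to change.** 1. Reconcile 22 with 17 in a participant flow: how many of the 17 come from each period, who was left out and why, and whether any woman is counted twice.
2. For both uterine lining and pregnancy, make the 8 PRP v 5 control women, kept in their randomised arms, the only between-arm description. Show pregnancy as counts.
3. Put the non-randomised PRP women in a separate single-arm descriptive column, with no contrast against the 5 controls. There are 14 by the Protocol; the number within the SAP's 17 depends on step 1.

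**Cost.** A few sentences in the SAP, one reconciliation and one re-cut table, needing only each woman's study period and allocated arm. No woman's data are discarded. The between-arm description falls from 22 to 13 women and the PRP figure becomes less precise: with the assumed counts, the exact interval is 3% to 65% for 2/8 against 7% to 50% for 4/17. The extra precision of the pooled figure comes from women with no randomised control, so it is not precision about the effect of PRP. The 8 v 5 comparison should still be labelled descriptive only.

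### The SAP's single PRP arm of 17 must mix randomised and self-selected women from two periods, the SAP does not say so, and the protocol's 8 + 14 does not give 17.

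*SAP*

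**What the plan says.** The protocol, under *Study Period 1: Randomized controlled trial*, gives "8 subjects randomized to PRP" and "5 subjects randomized to control". The same part, at the end of the account of the embryo-transfer cycle, gives the entry step: "If the lining is thin, patient will be randomized to control or study group".

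Under *Study period 2 (10/2/2018)* the design changes: "Prospective recruitment of patients opting for PRP (no randomization; all received intervention". The count there is "14 Subjects received PRP using the above protocol".

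The SAP's only statement on numbers is "We ultimately enrolled 17 subjects into the intervention arm and 5 subjects into the control arm". It names uterine lining as the primary outcome and pregnancy rate as the secondary, says the study was not powered for significance testing, and continues: "Accordingly, we have calculated and presented descriptive statistics of our baseline characteristics and study outomes". The summaries are means with standard deviations, and percentages. The SAP does not mention two periods, non-randomised entry, how the 17 are made up, or any split of the summaries by period or randomisation status.

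**The concern.** There are two linked problems.

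- **Composition.** The 5 controls match the Period 1 controls exactly, and Period 2 had none. The intervention arm of 17 is larger than the Period 1 PRP group, so it must include women who entered by choosing PRP. Calling the two groups the intervention and control arms hides this.
- **Count.** The protocol's PRP numbers do not add up to the SAP's, and no text explains why.

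One stated aim of the study is to examine what PRP does. Readers will set a PRP column of 17 beside a control column of 5 for baseline, lining and pregnancy. Any difference between the columns would then combine a possible PRP effect with the reasons women opted for PRP and with the change of period. Leaving out a test or a power claim does not remove that. Until the gap of 5 is explained, it is also unclear who contributes to each intervention-arm mean and percentage. If 17 is itself the wrong figure, the denominator changes too.

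**Working it through.** **Inputs**

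- Randomised to PRP, Period 1: 8 (protocol, Study Period 1)
- Randomised to control, Period 1: 5 (protocol, Study Period 1)
- Given PRP without randomisation, Period 2: 14 (protocol, Study period 2)
- Intervention arm 17, control arm 5 (SAP)

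**Step 1: try to reproduce 17.** Period 1 PRP alone gives 8. Period 2 alone gives 14. Together they give 8 + 14 = 22. None equals 17. Overall, 8 + 5 + 14 = 27, against 17 + 5 = 22 in the SAP. The gap is 22 − 17 = 5 for PRP and 27 − 22 = 5 overall.

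**Step 2: bound the composition.** Let r be the number among the 17 who were randomised to PRP. Then r ≤ 8 and 17 − r ≤ 14, so 3 ≤ r ≤ 8. The number not randomised to PRP is 17 − r, from 9 to 14.

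| Randomised to PRP | Not randomised to PRP | Share not randomised to PRP |
|---|---|---|
| 3 | 14 | 82.4% |
| 4 | 13 | 76.5% |
| 5 | 12 | 70.6% |
| 6 | 11 | 64.7% |
| 7 | 10 | 58.8% |
| 8 | 9 | 52.9% |

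**Step 3: allow for women counted in both periods.** Letting Period 1 PRP women or controls reappear in Period 2 leaves both ranges unchanged. A different quantity, women never randomised to either arm, could be as low as 4 of 17 (24%). That needs all 5 controls to have crossed over and to be counted in both arms: 9 − 5 = 4. The claim is therefore limited to women not randomised *to PRP*.

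**Step 4: possible explanations of the gap.** The documents do not settle which applies.

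| Reading | Arithmetic | Share not randomised to PRP |
|---|---|---|
| Five women counted in both periods | 8 + (14 − 5) = 17; 17 + 5 = 22 | 9/17 = 53% |
| The 8 is mis-stated (8 is the Period 1 total, 3 + 5) | 3 + 14 = 17 | 14/17 = 82% |
| The 14 is mis-stated | 8 + 9 = 17 | 9/17 = 53% |
| Five PRP women excluded | 22 − 5 = 17 | 9/17 to 14/17 = 53% to 82% |
| The 17 is mis-stated | 8 + 14 = 22 | 14/22 = 64% |

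Under every reading, more than half the arm was not randomised to PRP. Exclusion fits the wording poorly: the SAP's 17 is a number enrolled, while the protocol's 14 is a number treated.

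**Step 5: what the mixing could do.** This is an illustration with an assumed difference; the documents report none. If women not randomised to PRP differed in lining by 1 mm for reasons other than PRP, the arm mean would move by 1 mm × 9/17 = 0.53 mm up to 1 mm × 14/17 = 0.82 mm.

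**The case against.** The best defence is that this was a small descriptive pilot with feasibility among its aims. The SAP states no between-arm contrast, test or efficacy conclusion, and the protocol openly says Period 2 was not randomised. On that view the defect is a missing cross-reference and a missing split of the 17. The available text is also incomplete, and an overlap of five women would make the numbers agree exactly.

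Part of this stands.

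- The protocol's sentence "The only difference between the two groups will be the intrauterine infusion of PRP based on randomization" mainly describes care procedures within Period 1. It is weak support for a claim about comparability, and the point does not need it: self-selection follows from the Period 2 description alone.
- Under most readings the arm size is 17, and what is unknown is who the 17 are. The size itself changes only if 17 is mis-stated, but that cannot be ruled out.
- The contrast in entry routes should not be pressed too far. The thin-lining trigger sits in the embryo-transfer pathway, no randomisation point is given for the Asherman's pathway, and no Period 2 eligibility criteria are stated.
- That the gap is unexplained can be said only of the text available.

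The rest does not answer the concern. Disclosure in the protocol does not help a reader of the SAP, which merges the periods under one arm label. Overlap is stated nowhere, and it would still leave 9 of 17 not randomised to PRP. If the overlapping women were controls who later took PRP, the same women could appear in both columns, which makes disclosure more necessary.

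**Conclusion.** The concern holds and needs correction. On the documents' own counts, the intervention arm of 17 combines both periods, with 3 to 8 women randomised to PRP and 9 to 14 (53% to 82%) not. It stands beside 5 randomised controls, and the SAP says nothing of this. Five PRP women are unaccounted for (22 against 17).

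The 3-to-8 and 9-to-14 ranges assume that 8, 14 and 17 are all correct and that the 17 come from the protocol's two groups. If 17 is the wrong figure, the split is 8 and 14 of 22, or 64% not randomised to PRP. The conclusion that most of the arm was not randomised to PRP holds under each reading considered. The documents show neither an actual bias nor its direction.

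**What to change.** 1. Reconcile 8, 14 and 17 in the SAP. State how many of the 17 were randomised to PRP, whether any woman is counted in both periods or both arms, and the reason for any exclusion.
2. Show PRP-versus-control summaries of baseline, lining and pregnancy only for the Period 1 randomised set, by allocated group, using the reconciled numbers.
3. Report Period 2 in its own column as an uncontrolled single-arm series. Label any pooled column as non-randomised and supplementary.

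The cost is a count reconciliation, some SAP wording and one more table column. The real downside is coarser summaries: one pregnancy is 1/17 = 5.9 percentage points in the pooled arm, 1/8 = 12.5 in 8 women and 1/3 = 33.3 in 3, against 1/5 = 20 among the controls. If randomised women were left out of the 17, their outcomes would have to be retrieved or reported as missing; the documents do not show whether those data exist.
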